9. Evidence or self-report history of mobility disability requiring a walker, wheel chair, or inability to walk across a small room.
10. Evidence or self-report history of orthopedic limitations that would preclude them from participation in a dynamic exercise program
11. Evidence or self-report history of severe arthritis (either osteoarthritis or rheumatoid arthritis) that would preclude them from participation in a dynamic exercise program
12. Evidence or self-report history of untreated thyroid dysfunction.
13. Weight loss of > 10% in the last 3 months prior to screening
14. History of weight loss surgery.
15. Use of medications known to influence study outcomes, such as:
 - a. Insulin
 - b. Oral antidiabetic medications (e.g., metformin)
 - c. Corticosteroids within the past 14 days (topical or inhaled are allowed)
 - d. Beta-blockers
 - c. Anticoagulants
16. Allergy to lidocaine
17. Active smoking

18. Current consumption of > 14 alcoholic drinks per week based on self-report
19. Regular participation in resistance or aerobic exercise training within 3 months of initial screening
20. Absolute Contraindication to Exercise as Defined by the American College of Sports Medicine,¹⁶ including:
 - a. Resting diastolic blood pressure > 100 mm Hg
 - b. Resting systolic blood pressure > 180 mm Hg
 - c. Resting heart rate > 100 beats per min
21. Having a body weight greater than 440 pounds
22. Having medical implants such as a pacemaker or metal joint replacements
23. Having tattoos or permanent makeup completed <30 days prior to the visit
24. Recent (past 3 months) cancer diagnosis, undergoing immunotherapy, taking immune suppressants
25. Presence of allergies or infections requiring antibiotics within the past 14 days
26. Recent (past 3 months) major surgery on the abdomen, pelvis, or lower extremities
27. Any other condition that in the judgement of the Principal Investigator and/or the Medical Director of this protocol may interfere with study participation and adherence to the protocol.
28. Evidence or self-report history of severe depression in the last 5 years.

RECRUITMENT METHODS

Number of Subjects. We expect to screen about 150 potential volunteers, to recruit and study up to 45 subjects to complete at least 36 subjects (12/group) accounting for a 20% attrition rate (See Sample Size, Power Analysis and Randomization section for further details on sample size).

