Source of Subjects. The greater Baton Rouge community has between 30-40,000 adults 65 years of age or older. We will identify potentially eligible study subjects via advertising. Specifically, with the assistance of the PBRC Recruiting Core, we will recruit potential subjects from advertisements placed on the bulletin boards, electronic bulletin boards, social media, and in local and regional newspapers (e.g., the Advocate, the LSU Reveille,) and magazines. We will advertise on regional radio stations as needed. We will post flyers in senior housing establishments as well as attend senior expos. All recruitment materials will be approved by the IRB prior to their use.

SCREENING AND STUDY VISITS

Screening Visits.

Potentially eligible subjects will complete a screening visit, which we will split into two parts. We will try and schedule Part I and II on the same day, but these visits may be conducted on separate days.

Screening Visit, Part I (about 3 hours) will be conducted at PBRC and will include IRB approved written informed consent, review of inclusion/exclusion criteria, medical history, physical exam, vital signs, resting electrocardiogram, height, weight, fasting blood draw (~ 10 ml, 2 teaspoons), and Physical Activity Readiness Questionnaire for Everyone (PARQ+), the Short-Physical Performance Battery (SPPB),¹⁷ and Saint Louis University Mental Examination.¹⁸ We will peak oxygen consumption (VO₂ peak) using a cardiopulmonary exercise test¹⁶ in the Exercise Testing Core. *Prior to the completion of Part I of the screening visit, eligible subjects will be provided a map and directions on how to get to the LSU Exercise Physiology Laboratory and the School of Kinesiology Exercise Training Facility. There are reserved parking spots available through the LSU School of Kinesiology that will be reserved for Part II of the screening visit as well as study visits conducted in the LSU Exercise Physiology Laboratory or the School of Kinesiology Exercise Training Facility. We will also provide the subjects the contact information (office and cell phone number) of the study personnel assigned to meet them at each study visit and training session.*

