Exercise Test – VO₂ Peak (about 1 hour). Prior to the first exercise test, subjects will complete a physical exam, medical history, resting EKG which will be reviewed by [name] (Medical Investigator) and/or other qualified practitioner. Exercise test will only proceed if subject qualifies. We will use an incremental treadmill protocol with indirect calorimetry (Parvo-Medics TrueOne) to measure VO₂ peak at PBRC in the Exercise Testing Core.¹⁶ Subjects will be asked to initially walk at 1.5 miles per hour at 0% grade for 5 minutes. Following this initial warm-up, subjects will begin walking at self-selected brisk walking speed at 0% grade. Thereafter the speed will remain constant and the grade will increase by 2% every 2 minutes until

volutional exhaustion. Once this is reached, a 5 minute cooldown starting at 1.5 mph and 0% grade will be initiated. During the cool-down, the speed will be gradually lowered by 0.5 mph each minute until 0 mph is reached. We will assess heart rate continuously using a 12 lead EKG, while blood pressure and ratings of perceived exertion (RPE, Borg 6-20) will be assessed every 2 minutes. According to PBRC SOP 1303 for exercise testing, a physician will be available in the building and may be present at the time of testing should any complications arise. During the test, subjects will be told that they can lightly grip the hand rails at any time if it makes them feel more secure while walking. Stopping rules for this test are consistent with other exercise testing procedures performed in the Exercise Testing Core as described in SOP 1303. The exercise EKG will be read by the study physician for any signs of abnormalities and will be documented and reported to the PI and the study medical investigator. The medical investigator will contact the subject to discuss any abnormal findings, and with the subjects permission may contact the subject's physician to facilitate appropriate follow-up.

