
Resting Metabolic Rate (RMR) and Fuel Oxidation Before and After MMTT. Indirect calorimetry will be performed prior to and during each MMTT. Resting energy expenditure and substrate utilization will be assessed using the ParvoMedics, TruOne 2400 metabolic cart (Sandy, UT) calibrated with standard gas mixtures. A transparent plastic hood connected to the metabolic cart will be placed over the participant's head and calculations of energy expenditure and carbohydrate and fat oxidation rates will be made from expiratory gases diluted to produce a constant fraction of expired carbon dioxide (~1.0%). RMR measurements will be assessed before the MMTT and at 1 and 2 hours after ingestion of the mixed meal, each measurement will last about 30 minutes.

Muscle Biopsy Procedure (about 30 minutes). A *vastus lateralis* muscle biopsy will be performed using the technique of Bergstrom as described in SOP 906 from the PBRC Inpatient Unit by a trained medical professional. After cleansing the skin with povidone-iodine solution, the skin, adipose tissue and skeletal muscle fascia are anesthetized using < 5mL of a 50%/50% mixture of bupivacaine and lidocaine (final concentrations 1.0% and 0.125%). The skin is incised (0.75cm) with a #11 scalpel. The fascia fibers are separated with the blunt edge of the scalpel and the Bergstrom needle (4mm) inserted into the *vastus lateralis*. After suction is applied, approximately 500 mg of tissue is cut and removed. Four to 6 passes may be required to obtain a goal of 500 mg of muscle. Pressure is applied and the skin is closed with sterile tape.

Muscle Biopsy Processing and Storage. We will immediately place a portion of the muscle biopsy sample (~50-100 mg) in ice-cold (0-4 °C) relaxation and biopsy preservation buffer (BIOPS: 10 mM Ca⁺⁺-EGTA, 0.1 µM free Ca⁺⁺, 20 mM imidazole, 20 mM taurine, 50 mM K-MES, 0.5 mM DTT, 6.56 mM MgCl₂, 5.77 mM ATP, 15 mM phosphocreatine)³¹. This portion of the biopsy will be immediately transferred on ice (0-4 °C) to the LSU Exercise Physiology Laboratory for measurement of skeletal muscle OXPHOS using HRR (see Transport of Muscle Tissue and Blood). The BIOPS buffer has been shown to preserve the integrity of skeletal muscle OXPHOS measured using HRR for a minimum of 4 hours.³⁶ The remaining muscle will be flash-frozen in liquid nitrogen, transported to the LSU Exercise Physiology Laboratory on dry ice, and stored at -80°C (see Transport of Muscle Tissue and Blood).

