14. History of weight loss surgery.
15. Use of medications known to influence study outcomes, such as:
 - a. Insulin
 - b. Oral antidiabetic medications (e.g., metformin)
 - c. Corticosteroids
 - d. Beta-blockers

- c. Anticoagulants
- 16. Allergy to lidocaine
- 17. Active smoking
- 18. Current consumption of > 14 alcoholic drinks per week based on self-report
- 29. Regular participation in resistance or aerobic exercise training within 3 months of initial screening
- 20. Absolute Contraindication to Exercise as Defined by the American College of Sports Medicine,¹⁶ including:
 - a. Resting diastolic blood pressure > 100 mm Hg
 - b. Resting systolic blood pressure > 180 mm Hg
 - c. Resting heart rate > 100 beats per min
- 21. Having a body weight greater than 440 pounds
- 22. Having medical implants such as a pacemaker or metal joint replacements
- 23. Having tattoos or permanent makeup completed <30 days prior to the visit
- 24. Recent (past 3 months) cancer diagnosis, undergoing immunotherapy, taking immune suppressants, and presence of allergies or infections requiring antibiotics
- 25. Recent (past 3 months) major surgery on the abdomen, pelvis, or lower extremities
- 26. Any other condition that in the judgement of the Principal Investigator and/or the Medical Director of this protocol may interfere with study participation and adherence to the protocol

Source of Subjects. The greater Baton Rouge community has between 30-40,000 adults 65 years of age or older. We will identify potentially eligible study subjects via advertising. Specifically, we will recruit potential subjects from advertisements placed on the bulletin boards, electronic bulletin boards, social media, and in local and regional newspapers (e.g., the Advocate, the LSU Reveille,) and magazines. We will advertise on regional radio stations as needed. We will post flyers in senior housing establishments as well as attend senior expos.

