11. **Muscle Biopsies.** A *vastus lateralis* muscle biopsy will be performed using the technique of Bergstrom as described in SOP 906 from the PBRC Inpatient Unit by a trained Nurse Practitioner or physician. For *vastus lateralis* muscle biopsies, the risks are mild to severe pain, soreness, bruising and a small scar are common risks. There is a small risk of a hematoma (collection of blood in the tissue) or infection at the biopsy site. There is also a slight risk that a superficial nerve may be cut; the nerve may heal, or it may result in a permanent loss of sensation in the skin at the biopsy site. Sterile technique will be used to minimize infection risks and the biopsy site will be monitored closely. To reduce the risk of hematomas and bleeding, we ask that subjects stop taking anticoagulants, non-steroidal anti-inflammatory (NSAIDs), and aspirin for a week before and after the biopsy procedure. We will exclude individuals who cannot stop their anticoagulants. Previous data suggest that the rates of adverse events following a percutaneous muscle biopsy in older adults (60-76 years) are similar to those of younger adults.⁴¹ Moreover, [name] previously conducted a study at PBRC that included biopsies in elderly adults (70-84 years) with no serious adverse events.⁴² The PI has led and been involved in multiple studies that included muscle biopsies in both young (18-30) and older adults (65-85 years).^{15, 43-45}
12. **Archive of Biological Sample (blood and muscle biopsy tissue).** The primary risk to subjects who donate bio-samples to be banked for future research (molecular in this case) is the risk of loss of confidentiality and/or privacy. Most banks need to maintain a link between the identities of donors and coded specimens to be able to collect valuable clinical follow-up information about the donor. We will, however, create and maintain a firewall between the source and the researcher so that the protected health identifiers are never given to the researcher(s). Storage and disposal of tissue will be conducted in a manner conforming to the appropriate care and handling of biological specimens as outlined through the Institutional Biohazard Committee Guidelines.

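### Exclusion 16 covers allergy to lidocaine only, although the muscle biopsy anaesthetic also contains bupivacaine

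*Combined protocol and SAP*

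**What the plan says.** **The drugs given.** Under Detailed Methods and Analysis, the Muscle Biopsy Procedure section states that the skin, fat and fascia are "anesthetized using < 5mL of a 50%/50% mixture of bupivacaine and lidocaine (final concentrations 1.0% and 0.125"%). Table 1 schedules the biopsy at V2 and again at V5. Only the carbon-13 spectroscopy is labelled optional, not the biopsy.

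**The allergy rule.** Exclusion 16 in Study Population reads "Allergy to lidocaine". The second copy of the list, in section 1a of the safety-monitoring provisions, uses the same words under the same number.

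**Other wording that might apply.**
- Exclusion 25 in Study Population is "Presence of allergies or infections requiring antibiotics within the past 14 days". The matching part of exclusion 24 in section 1a is "presence of allergies or infections requiring antibiotics", without the 14-day limit.
- The closing criterion of each list (27 in Study Population, 26 in section 1a) is a catch-all: "Any other condition that in the judgement of the Principal Investigator and/or the Medical Director of this protocol may interfere with study participation".
- Screening Visit, Part I includes "review of inclusion/exclusion criteria, medical history, physical exam, vital signs, resting electrocardiogram".
- The VO₂ peak section adds a clinical review: "Prior to the first exercise test, subjects will complete a physical exam, medical history, resting EKG which will be reviewed by" the Medical Investigator and/or another qualified practitioner.
- The Muscle Biopsies item under Potential Risks says that the procedure is done "as described in SOP 906 from the PBRC Inpatient Unit by a trained Nurse Practitioner or physician".

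**The concern.** The authors decided that allergy to a local anaesthetic used at the biopsy should keep a person out of the study. Having made that decision, they named one of the two agents in the mixture. A coordinator working down the list would find no specific item that stops a person allergic only to bupivacaine.

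What is at stake is an allergic reaction to a drug injected for a research procedure from which the subject gains nothing clinically. The risk can be avoided by asking the right question at screening. Nothing in the trial's inference depends on it.

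**Working it through.** No sample size, power or error-rate calculation is involved. The check sets the procedure beside the eligibility text.

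**1. Drugs injected against drugs covered.**

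| Drug in the biopsy mixture | Exclusion 16, Study Population | Exclusion 16, section 1a |
|---|---|---|
| Lidocaine | named | named |
| Bupivacaine | not named | not named |

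Two drugs are injected and one is covered, so 2 − 1 = 1 is uncovered, in both lists. Bupivacaine appears once in the whole document, in the biopsy procedure.

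**2. Does another specific criterion cover bupivacaine?** The only other allergy wording is in exclusion 25 (24 in section 1a). It pairs allergies with infections and ties them to antibiotic use; it names no anaesthetic. Reading it to cover every allergy would make exclusion 16 redundant, which cannot be what the authors meant.

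**3. Does a general safeguard cover it?**
- The catch-all criterion can be used to exclude such a person, but it depends on judgement and on the allergy already being known.
- The medical history may bring the allergy out, but no text tells staff to ask about bupivacaine or about local anaesthetics generally. The clinical review in the VO₂ peak section is described as clearance for the exercise test, not for the biopsy.
- SOP 906 may contain an allergy check. It is not among the documents, so this can be neither confirmed nor ruled out. A check made at the biopsy would come at V2, after screening and V1 are finished.
- The Muscle Biopsies risk text lists pain, soreness, bruising, scarring, haematoma, infection and nerve injury. It does not mention a reaction to the anaesthetic, so it gives no second prompt.

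**4. Exposure.** A completer has 2 biopsies (V2 and V5). With the planned 36 completers that is 36 × 2 = 72 biopsies under the mixture, plus those in subjects who do not finish. This measures exposure, not risk: the documents give no frequency of bupivacaine allergy, so no number of affected subjects is estimated.

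**5. When an added exclusion would act.** The order is screening, V1, V2 with the first biopsy, then randomisation. A person excluded at screening has been neither injected nor allocated, so the number of randomised subjects lost through the change is 0.

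**The case against.** The strongest reply is that the protection already exists in substance. The catch-all is itself a stated criterion, and a known allergy to an agent used in a scheduled procedure fits it well; what is missing is an explicit example, not the power to exclude. Someone unaware of the allergy is missed under either wording, and someone who mentions it at the medical history can be excluded now. The rewording therefore helps only a person who knows of the allergy, does not volunteer it, and would report it if asked by drug name. SOP 906 and the screening forms, which cannot be seen here, may already ask. Nor does the protocol name every agent: povidone-iodine and the meal drink have no allergy exclusion.

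Much of this stands. It shows that a miss is unlikely, and it limits the point to a mismatch in the written rule; it does not allow a claim that nobody asks about bupivacaine. The volume is also capped below 5 mL.

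It does not remove the mismatch. The same catch-all, history and SOP apply to lidocaine, yet the authors still listed lidocaine by name. Having chosen an explicit rule for the biopsy anaesthetic, they need it to match the anaesthetic used. The comparison with povidone-iodine is weaker, because the plan sets no allergy rule there to be left half-complete.

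**Conclusion.** The concern holds, as a minor safety and eligibility correction. Exclusion 16 names one of the two anaesthetics injected at a scheduled, non-optional biopsy, and both copies of the list have the same gap. For bupivacaine, exclusion rests on a general history and clinical judgement instead of a stated criterion.

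Confidence in the mismatch is high, since it rests on the text alone. How much practical protection is missing is less certain, because it depends on SOP 906 and on the screening forms, neither of which is in the documents. No reaction rate is assumed. Endpoints, sample size, randomisation and analysis are unaffected.

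**What to change.** - Reword exclusion 16 in both lists (Study Population and section 1a) to *allergy to lidocaine or bupivacaine*.
- Ask about both drugs by name when the medical history is taken at Screening Visit Part I.
- Ask any subject already enrolled when the change is made the same question before the next biopsy.

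The cost is one wording change made in two places, one screening question and, rarely, an extra exclusion before randomisation. Visits, endpoints, sample size and analysis stay as they are.

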Screening Visit, Part II (about 2 hours) will be conducted in LSU Exercise Physiology Laboratory and will include height, weight, the completion of the International Physical Activity Questionnaire-Elderly,¹⁹ Sedentary Behavior Questionnaire,²⁰ and PROMIS Physical Function Questionnaire^{21, 22}, and the Pittsburgh Fatigability Questionnaire. We will also measure height and weight. We will measure isokinetic strength and endurance of the knee extensors (Biodek System 3) and the 1-repetition maximums (1-RMs)

for the knee extension, leg press, and chest press. Note: the 1-RM measurements may be performed prior to your regularly scheduled exercise session during the first and last week of the intervention. We will also measure grip strength using a hand dynamometer.

Baseline Physical Activity Monitoring. At the end of part II of the screening visit, all subjects who are deemed eligible to continue onto the pre-training visits described below will be provided two devices to measure their physical activity leading up to their pre-intervention testing. A wrist-worn physical activity monitor (Actigraph, GT9X) will be issued to the subjects to wear 24-h/d for 7-days (± 3 days) prior to their pre-training visits to quantify objectively their PA and ST. Subjects will also be asked to wear a second physical activity monitor (Actigraph, GT9X) on their thigh 24-h/d for 7-days (± 3 days). Subjects will be asked to return their physical activity monitors during the Pre-training Visit 1 (V1). In the event that a subject is deemed ineligible after part II of the screening visit, we would request that the subject return his/her physical activity monitors at their earliest convenience. We will screen raw data from these monitors for periods of valid wear-time with a required minimum wear-time of 10 h per valid wear-day and 4 valid wear-days per week.^{23, 24} We will use standard algorithms to characterize the patterns of PA and ST.²⁵

Baseline Dietary Record. Subjects will be asked to record their dietary intake for the 24 hrs prior to their pretraining visit 1. They also will be asked to replicate their dietary intake before posttraining visit 4. Moreover, they will be asked to refrain from consuming caffeine or participating in vigorous exercise 48 hours prior to these visits.

Pre-training Visits 1 (V1). (About 5 hours). V1 will be scheduled at least 7 days after screening visit Part II.

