Exercise Interventions. After completing V2, we will randomize the subjects to one of three 16-week interventions: (i) RE, (ii) REALPA breaks in ST, or (iii) RE+AE (**Figure 3**). The RE+AE group serves as the standard of care. The RE group will complete supervised RE (2 x/wk). The REALPA breaks in ST group will complete a supervised RE (2 x/wk) and regular unsupervised LPA breaks in ST (5 d/wk, 6x10 min breaks/d at 2 METS (~30-40% VO_2 peak), ~500 kcal/wk above resting metabolism). The RE+AE group will complete supervised RE (2 x/wk) and calorically matched moderate intensity AE (3 d/wk, 50 min/session at 4 METS (~60-75% VO_2 peak), ~500 kcal/week above resting metabolism). The RE component for all 3 groups will consist of 3 sets of 10-12 repetitions to failure for a total of 8 exercises targeting the large muscle groups (**Table 2**). The AE component for the RE+AE group will consist of treadmill walking at ~4 METs for 50 min

(Table 2). The RE and AE sessions will take place in LSU School of Kinesiology's Exercise Training Facility under direct supervision (Drs. [name], [name], and [name] with the assistance of trained graduate students). All supervised exercise sessions will include a 5 minute warm-up and cool-down on either a bike or treadmill. We will provide subjects flexibility on the days per week that they can complete their exercise sessions. Note: The start of the exercise intervention will be at least 5 days post V2 to allow for adequate recovery from the muscle biopsy, but no more than 6 weeks after V2. Up to 2 weeks may be added to a subjects exercise intervention, to allow for potential make-up of missed exercise sessions and to provide flexibility for scheduling study visits.

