[name] (LSU) and [name] (PBRC). We will screen all data for distributional properties (mean, median, range) and departures from normality prior to substantive analyses. To test the main effects of time, treatment, and their interaction on the primary outcomes, we will use mixed-effects two-way Analysis of Variance (ANOVA) models ($\alpha=0.05$). The models will include parameters to estimate the main effects of time (pre- and post-training) and treatment (RE, REALPA breaks in ST, RE+AE) on the dependent variables. We will use *Fisher's Least Significant Differences test* to examine within and between group mean differences ($\alpha=0.05$). We will test all models for the main effect of sex. If the main effect of sex is significant, we will perform additional exploratory analyses stratified by sex. Other covariates that may be included in the models include race, change in body weight, and baseline SPPB scores. We will also compare adherence rates across the study groups.

Sample Size, Power Analysis and Randomization. We will use the data collected in this **pilot study** to estimate effect sizes for the primary and secondary outcomes, which we will use to inform our power analyses for a follow-up R01 application designed to test the efficacy of our novel exercise intervention on skeletal muscle and cardiometabolic health in sedentary older adults. We will use a fixed sample size of 12 subjects per group, because increasing the sample size above 12 (i.e., 12 to 15) has diminishing benefit in estimations effect sizes and 95% confidence intervals often referred to as the “rule of 12”.^{39, 40} Thus, we will recruit up to 15 subjects per group to account for a 20% attrition rate. The NIH’s Clinical and Translational Science Awards Biostatistics, Epidemiology, and Research Design (BERD) units recommend 12 subjects per group for estimating effect sizes and 95% confidence intervals.³⁹ Following baseline testing, we will randomize the study subjects to one of the three interventions using a randomized, permuted, block design stratified by sex and race.

PROVISIONS TO MONITOR THE DATA TO ENSURE THE SAFETY OF SUBJECTS

This Human Subjects Research meets the definition of a Clinical Trial. This study does not involve major risk to subjects. Efforts to minimize the potential risks of the assessment methods and outcome variables include frequent monitoring by the investigators to assure that no volunteer suffers any adverse effects from participating in the research.

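### The planned time-by-treatment test is valid but does not adjust for each outcome's own baseline, and the exploratory sex analyses are triggered mainly by a difference in level, not in response

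*Combined protocol and SAP*

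**What the plan says.** Under Data Management and Primary Statistical Analyses: "To test the main effects of time, treatment, and their interaction on the primary outcomes, we will use mixed-effects two-way Analysis of Variance (ANOVA". Pre- and post-training are the two levels of the time factor, so the baseline value enters as a response and not as a covariate. Group means are then compared by Fisher's least significant difference at 0.05.

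On covariates: "Other covariates that may be included in the models include race, change in body weight, and baseline SPPB scores". The outcome's own baseline is not listed. On sex, only a main effect is tested: "If the main effect of sex is significant, we will perform additional exploratory analyses stratified by sex". No sex-by-treatment or sex-by-time term is described.

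Under Sample Size, Power Analysis and Randomization, the pilot's data are to be used "to estimate effect sizes for the primary and secondary outcomes, which we will use to inform our power analyses" for a follow-up application. The fixed size of 12 per group is defended because "increasing the sample size above 12 (i.e., 12 to 15) has diminishing benefit" for estimating effect sizes and their intervals. Allocation uses a permuted "block design stratified by sex and race".

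On timing, the Exercise Interventions section says: "After completing V2, we will randomize the subjects to one of three 16-week interventions". Before that point, Screening Visit Part II includes this step: "We will measure isokinetic strength and endurance of the knee extensors". DXA, fasting bloods and the mixed meal test are done at V1.

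**The concern.** The pilot exists to deliver an effect size and interval for the next trial, so the width of the REALPA-minus-RE interval is its main product. A pre/post interaction subtracts the baseline in full. When r is well below 1, this carries more baseline noise into the contrast than adjustment would. Any chance imbalance at baseline also moves the estimate that is passed to the next application. The variable that would help is already measured before randomisation. The plan instead names one covariate, change in body weight, that is measured after it.

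The sex rule raises a different issue. A main effect of sex in a pre/post model mostly asks whether men and women have different strength, mass or lipids on average. The question of interest is whether they respond differently to the interventions. A gate on the first question can open when there is nothing to find and stay shut when there is. No primary conclusion depends on it.

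**Working it through.** **1. The plan's own figure.** 12/(1 − 0.20) = 15 per group and 36/(1 − 0.20) = 45 in total, as stated. The 12 is a cited rule of thumb. The documents give no SD, effect size, power or r, so everything below is in SD units over an assumed range of r.

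**2. What the interaction estimates.** With complete pre and post data it equals the difference in mean change. On one simulated data set both routes gave −0.3314 with standard error 0.264. Simulated type I error was 4.7% to 5.4% for r from 0.5 to 0.9, and the estimates were unbiased.

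**3. Variance.** Per subject, a change score has variance 2(1 − r) and a baseline-adjusted post value has 1 − r². The ratio is (1 + r)/2 = 0.65, 0.75, 0.85, 0.95 and 0.975 at r = 0.3, 0.5, 0.7, 0.9 and 0.95. Ignoring degrees of freedom, 12 adjusted completers per arm are worth 12/ratio = 18.5, 16.0, 14.1, 12.6 and 12.3 with the change contrast. A chance baseline imbalance of one standard error, √(2/12) = 0.41 SD, shifts the change contrast by (1 − r) × 0.41, which is 0.20 SD at r = 0.5 and 0.04 SD at r = 0.9.

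**4. Interval half-widths.** Mean 95% half-width for REALPA minus RE in 20,000 simulated trials per r (three arms of 12, six per sex per arm, two race levels, no sex gap, all assumed). Residual degrees of freedom are 36 − 3 = 33, then 32, then 30.

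| r | change contrast | + own baseline | + baseline, sex, race | change in width (last vs first) |
|---|---|---|---|---|
| 0.3 | 0.975 | 0.800 | 0.802 | −18% |
| 0.5 | 0.824 | 0.726 | 0.728 | −12% |
| 0.7 | 0.638 | 0.598 | 0.600 | −6% |
| 0.9 | 0.369 | 0.365 | 0.366 | −0.8% |
| 0.95 | 0.261 | 0.262 | 0.263 | +0.8% |

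The gain comes from the baseline. With a 1 SD sex gap, adding the strata to baseline takes the half-width from 0.748 to 0.727 at r = 0.5 and from 0.608 to 0.600 at r = 0.7, and leaves it at 0.366 at r = 0.9.

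**5. Against going from 12 to 15 per arm.** Half-width is proportional to t/√n: 2.0345/√12 = 0.587 (33 df) against 2.0181/√15 = 0.521 (42 df), which is 11.3% narrower. Baseline adjustment matches this only up to r of about 0.5.

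**6. Allowing for drop-outs.** If 15 per arm start, 12 finish, and the mixed model keeps all baseline records, the planned contrast has variance proportional to (1 − r²)/12 + (1 − r)²/15. At r = 0.5 that is 0.0625 + 0.0167 = 0.0792, against 0.0625 adjusted, and √(0.0625/0.0792) = 0.889, or 11% narrower. Before the cost in degrees of freedom, the gain at r = 0.3, 0.5 and 0.7 falls from 19%, 13% and 8% (complete data) to 16%, 11% and 6%.

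**7. Sex trigger, 18/18 split assumed.**
- Level gap only, no difference in response: noncentrality = gap/√(2/18) = 1.5, 3.0 and 4.5 for gaps of 0.5, 1.0 and 1.5 SD. On 34 df the test fires in 31%, 83% and 99% of trials. At a 12/24 split the figures are 28%, 79% and 98%.
- Response only: a REALPA effect of 0.8 SD in one sex with no level gap enters the sex main effect as 0.8 × 1/3 (one arm of three) × 1/2 (one time of two) = 0.13 SD. Simulation gives firing in about 7% of trials, against 5% by chance. At r = 0.8 a direct sex-by-treatment test of change detects this effect in 32%.
- A treatment-by-sex estimate has a 95% half-width of 1.46, 1.21 and 0.74 SD at r = 0.5, 0.7 and 0.9 (six per sex per arm).

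**The case against.** The strongest reply is that nothing here is an error. The planned contrast is valid, and choosing between it and baseline adjustment is a matter of efficiency. That stands. A reader might infer that the planned test is biased, or that the plan ignores or forbids baseline adjustment. The documents do not support this: randomisation makes the change contrast unbiased, the baseline is in the model as a response, and the covariate list is permissive.

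Second, the gain depends on an r that the documents do not give. At 0.9 or above there is no useful gain, and no outcome has been shown to sit lower. That also stands. But the primary outcomes range from DXA mass to lipids and meal tolerance, so one r need not fit all of them, and the loss at 0.95 is under 1%.

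Third, the equivalence with a change score needs complete data, while the plan expects 20% attrition and a mixed model. This is right and reduces the gain as in step 6. The documents do not say whether drop-outs' baselines are kept.

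Fourth, the sex analyses are labelled exploratory, and with a large level gap the gate usually opens anyway. Both are true, and the replacement estimate is itself imprecise. A reader might also infer that the trigger has nothing to do with response. It averages pre and post, so it picks up a diluted part of any response difference and is nearly, not wholly, insensitive to it.

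**Conclusion.** The planned interaction can stand as a valid test. The plan would be better if it conditioned on the baseline it already collects. At 12 completers per arm the gain in interval width is about 18%, 12%, 6% and under 1% at r = 0.3, 0.5, 0.7 and 0.9, with a loss under 1% at 0.95. It is somewhat less if drop-outs' baselines are kept, and comparable to recruiting 15 per arm only up to r of about 0.5. These figures rest on an assumed r, normal data, equal arms and two race levels.

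The sex trigger mainly detects level: about 83% firing on a 1 SD gap with no difference in response, and about 7% on a 0.8 SD REALPA effect in one sex only with no gap, at an assumed 18/18 split. The consequence is limited to exploratory output.

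A reader might infer that the within-group changes listed under Study Endpoints should be demoted. This point gives no ground for that, and they can stay as they are. The changes are worth making because they cost little, not because a conclusion fails without them.

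**What to change.** 1. Estimate REALPA minus RE, with its 95% interval, from the post value on treatment, the outcome's own baseline and the randomisation factors sex and race, or from a mixed model with baseline means constrained equal across arms. The second form can also use drop-outs' baseline records.
2. Fix that covariate set in advance. Leave change in body weight out of it, because it is measured after randomisation.
3. Keep the planned time-by-treatment interaction as a sensitivity analysis.
4. Report the observed pre-post correlation for each primary outcome, since the next trial's power calculation will need it.
5. Drop the main-effect-of-sex trigger. Report an exploratory treatment-by-sex estimate of change with its 95% interval, whatever the main effect of sex, and say that it is imprecise.

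The cost is a few sentences and a few lines of code, with no new data. Residual degrees of freedom go from 33 to 30 if race has two levels. The documents do not give the number of levels, and each further level costs one more. For the primary strength outcome the baseline should be the isokinetic test at screening: the protocol allows 1-RM testing in the first intervention week, which falls after randomisation.
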